9.3. Changes to Final Study Protocol

All protocol amendments must be submitted to the ethics committee and regulatory authorities if required by local law. Protocol modifications that affect patient safety, the scope of the investigation, or the scientific quality of the study must be approved by the ethics committee before implementation of such modifications to the conduct of the study. If required by local law, such modifications must also be approved by the appropriate regulatory agency prior to implementation.

However, Biogen may, at any time, amend this protocol to eliminate an apparent immediate hazard to a patient. In this case, the appropriate regulatory authorities will be notified subsequent to the modification.

In the event of a protocol modification, the patient ICF may require similar modifications (see Sections [9.1](#) and [9.2](#)).

9.4. Subject Data Protection

Prior to any data collection under this protocol, eligible patients must also provide all authorizations required by local law (e.g., PHI authorization in North America).

The patient will not be identified by name in the CRF or in any study reports and these reports will be used for research purposes only. Biogen, its partner(s) and designee(s), ethics committees, and various government health agencies may inspect the records of

CONFIDENTIAL

The information contained herein may not be used, disclosed, or published without the written consent of Biogen MA Inc.

this study. Every effort will be made to keep the patient's personal medical data confidential.

In order to maintain patient confidentiality, each patient will be assigned a unique patient identifier upon study enrollment. This patient identifier will be used in place of patient name for the purpose of data analysis and reporting. For patients who participated in Study 105MS302 or Study 105MS303, the unique identifier assigned to the patient for the trials will be used to link data collected as part of this study with data from Study 105MS302 and Study 105MS303.

Medical record number or other local reference identifiers are not collected as part of the database. All parties will ensure protection of patient personal data and will not include patient names on any study forms, reports, publications, or in any other disclosures, except where required by law. In accordance with local regulations in each of the registry countries, patients will be informed about data handling procedures and asked for their consent. Data protection and privacy regulations will be observed in capturing, forwarding, processing, and storing patient data. Every effort will be made to protect participant confidentiality according to the Directive 95/46/EC on the protection of individuals, and in compliance with Safe Harbor privacy principles.

The database will be housed at IQVIA in a physically and logically secure computer system maintained by IQVIA in accordance with a written security policy. The system meets approved established standards for the security of health information and is validated. The system also meets the standards of ICH guidelines E6R1 regarding the handling of electronic study data and is available for audit upon request. Patient confidentiality will be strictly maintained.

9.5. Internal Safety Review

Applicable personnel at Biogen will review all SAEs on a regular basis.

9.6. Compensation for Injury

Biogen maintains appropriate insurance coverage for clinical trials and will follow applicable local compensation laws.

9.7. Conflict of Interest

The Prescribing Physicians should address any potential conflicts of interest (e.g., financial interest in Biogen) with the patient before the patient makes a decision to participate in the study.

CONFIDENTIAL

The information contained herein may not be used, disclosed, or published without the written consent of Biogen MA Inc.

10. SAFETY DEFINITIONS, RECORDING, REPORTING, AND RESPONSIBILITIES

Throughout the course of the study, every effort must be made to remain alert to possible AEs. If an AE occurs, the first concern should be for the safety of the patient. If necessary, appropriate medical intervention should be provided.

Each patient or their legally authorized representative and/or main caregiver must be given the names and telephone numbers of site staff for reporting AEs and medical emergencies.

10.1. Definitions

10.1.1. Adverse Event

An AE is any undesirable experience associated with the use of a medical product in a patient. An AE can therefore be any unfavorable and unintended sign (including an abnormal laboratory finding), symptom, or disease temporally associated with the use of a medicinal product, whether or not related to the medicinal product. A pre-existing condition that worsens in severity would also be considered an AE.

10.1.2. Serious Adverse Event

An SAE is any untoward medical occurrence that at any dose:

- results in death
- in the view of the Prescribing Physician, places the patient at immediate risk of death (a life-threatening event); however, this does not include an event that, had it occurred in a more severe form, might have caused death
- requires inpatient hospitalization or prolongation of existing hospitalization
- results in persistent or significant disability/incapacity, or
- results in a congenital anomaly/birth defect.

All malignancies should be considered serious and reported as SAEs.

An SAE may also be any other medically important event that, in the opinion of the Prescribing Physician, may jeopardize the patient or may require intervention to prevent one of the other outcomes listed in the definition above. (Examples of such medical events include allergic bronchospasm requiring intensive treatment in an ER or convulsions occurring at home that do not require an inpatient hospitalization.)

10.2. Monitoring and Recording Events

10.2.1. Adverse Events

The Prescribing Physician should review all AEs experienced by a patient from the time the patient signs the ICF and record the following events in the eCRF:

CONFIDENTIAL

The information contained herein may not be used, disclosed, or published without the written consent of Biogen MA Inc.

- SAEs
- AEs (including laboratory abnormalities) leading to discontinuation of Plegridy treatment
- AEs of special interest (FLS, ISRs)

All other non-serious AEs will not be collected as part of this study. The process for reporting these non-serious AEs should follow spontaneous postmarketing rules as per local regulations.

10.2.2. Serious Adverse Events

Any SAE experienced by a patient between the time the patient signs the ICF and before study completion or premature study withdrawal, or within 30 days of discontinuation of Plegridy, is to be recorded on an SAE Form, regardless of the event's relationship to Plegridy. It is the responsibility of the Prescribing Physician to report pharmacovigilance information for other MS products per local regulations. For patients who discontinue treatment but continue to participate in the study, any serious events, including malignancies that occur within 30 days after the last dose of Plegridy will be treated as SAEs and reported on an SAE form. For reporting timelines and procedures, see Section [10.2.4](#).

MS relapses will not be automatically reported as an SAE unless the relapse was fatal or, in the opinion of the Prescribing Physician, the relapse was complicated by other SAEs.

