8.1.1. Primary Endpoints

Safety of Plegridy will be evaluated by assessment of the incidence proportion and incidence rate of SAEs.

Effectiveness of Plegridy on cNEDA will be evaluated by assessment of the proportion of patients with no relapses and no disability progression.

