8.2.4.4. Treatment

Plegridy will be prescribed to patients by their Prescribing Physician under routine clinical practice according to the indication and dosing regimen in the local package insert.

CONFIDENTIAL

The information contained herein may not be used, disclosed, or published without the written consent of Biogen MA Inc.

This is an observational study of real-world treatment practices and long-term effectiveness and safety in this population of patients with RMS. This protocol does not recommend the use of any specific treatments. No study medication is provided as a result of participation.

Patients who discontinue treatment with Plegridy will continue to be followed for the duration of the study or until death, withdrawal, or until they are lost to follow-up. The Prescribing Physician will record the primary reason for Plegridy discontinuation, if applicable. Information will be collected at the time of a routine clinical visit following [Table 4](#) and as described in [Section 8.3](#) through 30 days after last dose.

It should be noted that patients who discontinue treatment with Plegridy should continue to be followed in the study. These patients are allowed to restart Plegridy at any time during the study. Once a patient has restarted Plegridy, the information collected should follow [Table 4](#) and as described in [Section 8.3.3](#).

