8.2.4.5. Post-Treatment

For patients who discontinue treatment with Plegridy, all follow-up visits will be conducted according to local clinical practice. Patients' participation in the study is independent of potential stopping treatment with Plegridy. Analysis of this patient data will be part of the exploratory analysis.

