8.6.4.2. Methods of Analysis

The incidence and incidence rate of all reported SAEs and AEs will be summarized by Medical Dictionary for Regulatory Activities (MedDRA) system organ class and preferred term. Incidence is defined as the proportion of patients with a given event out of the number of patients in the analysis population. Incidence rate is defined as the number of patients with a given event adjusted for the duration of follow-up for the particular event (e.g., incidence rate per 100,000 per years). Ninety-five percent CIs for incidence and incidence-rate point estimates will be calculated using the binomial distribution and the Poisson distribution, respectively.

Incidence of SAEs and AEs will be stratified by event severity and by relationship to treatment with Plegridy. AEs leading to discontinuation of Plegridy will be summarized separately. Analyses of SAEs and AEs may also be described by characteristics of the sites, Prescribing Physicians, and/or patient subgroups defined by appropriate demographic and/or baseline prognostic factors, and/or concomitant medication exposure (e.g., concomitant MS therapies). Analyses may also be stratified by duration of Plegridy treatment or study duration. Specific subgroup analyses will be described in the SAP.

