10.2.4. Immediate Reporting of Serious Adverse Events

In order to adhere to all applicable laws and regulations for reporting an SAE, the study site must formally notify IQVIA within 24 hours of becoming aware of the SAE. It is the Prescribing Physician's responsibility to ensure that the SAE reporting information and procedures are used and followed appropriately.

Reporting Information for SAEs

Any SAE that occurs between the time the patient signs the ICF and study completion or premature study withdrawal must be reported to IQVIA within 24 hours of the study site becoming aware of the event. For patients who discontinue treatment but continue to participate in the study, any SAE occurring within 30 days after the last dose of Plegridy will be treated as an SAE and reported within 24 hours of the study site becoming aware of the event.

A report ***must be submitted*** to IQVIA regardless of the relationship to Plegridy. It is the

CONFIDENTIAL

The information contained herein may not be used, disclosed, or published without the written consent of Biogen MA Inc.

responsibility of the Prescribing Physician to report pharmacovigilance information for other MS products per local regulations.

To report initial or follow-up information on an SAE, please refer to the Study Reference Manual for information on faxing the completed SAE form.

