10.2.4.1. Deaths

Death is an outcome of an event. The event that resulted in death should be recorded and reported on the appropriate CRF within 24 hours of the study site becoming aware of the event. All causes of death must be reported as SAEs. The Prescribing Physician should make every effort to obtain and send death certificates and autopsy reports to IQVIA.

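### The protocol gives two conflicting windows for capturing SAEs after Plegridy is stopped, and the denominator of the primary SAE rate is tied to neither

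*Protocol*

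**What the plan says.** **Endpoint.** Section 8.1.1: "Safety of Plegridy will be evaluated by assessment of the incidence proportion and incidence rate of SAEs". Follow-up lasts up to 60 months whether or not Plegridy is continued (8.1, 8.2.4, 8.6.7).

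**Longer window.** Section 10.2.2 opens with "Any SAE experienced by a patient between the time the patient signs the ICF and before study completion or premature study withdrawal", and 10.2.4 says "Any SAE that occurs between the time the patient signs the ICF and study completion or premature study withdrawal must be reported to IQVIA". Section 16.1 says that clinical data are captured whatever treatment is chosen, and Table 4 shows SAEs as one continuous arrow. Section 10.2.4.1 adds "All causes of death must be reported as SAEs", with no time limit.

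**Shorter window.** For patients who discontinue but remain in the study, 10.2.2 says "any serious events, including malignancies that occur within 30 days after the last dose of Plegridy will be treated as SAEs", and 10.2.4 repeats the rule. Section 8.2.4.4 says information is collected "through 30 days after last dose", pointing to all of Section 8.3. Section 8.2.4.9 has the same paragraph but points to 8.3.4, Laboratory Assessments.

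**Analysis.** Section 8.6.4.2: "Incidence rate is defined as the number of patients with a given event adjusted for the duration of follow-up for the particular event". The incidence proportion is patients with the event over patients in the analysis population. On data after discontinuation, 8.2.4.5 says "Analysis of this patient data will be part of the exploratory analysis".

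**The concern.** Patients who stop Plegridy but stay in the study are already covered by the longer rule. For them the 30-day sentence is therefore either redundant or a limit, and a site could reasonably take it as a limit, the more so as it names malignancies expressly. Another site, reading the opening sentence or Table 4, will report to study end. Both comply.

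This is the collection rule for a primary endpoint in a study whose purpose is long-term safety. Three things are at stake:

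- The SAE rate is diluted if off-treatment time is counted but its events are not collected.
- The SAE proportion loses later events, and no choice of person-time restores them.
- If practice differs between sites, ascertainment is uneven and cannot be corrected without knowing which rule each site used.

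Missed events can only lower the counts.

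**Working it through.** **1. The passages side by side**

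| Place | SAEs or data collected after Plegridy is stopped |
|---|---|
| 10.2.2 and 10.2.4, opening rule | to study completion or withdrawal |
| 10.2.2 and 10.2.4, rule for patients who discontinue | 30 days after last dose |
| 8.2.4.4 | 30 days after last dose (Section 8.3) |
| 8.2.4.9 | 30 days after last dose (Section 8.3.4) |
| 16.1 and Table 4 | throughout, regardless of treatment |
| 10.2.4.1 (deaths) | no time limit |
| 8.6.4.2 (denominator) | follow-up for the event; end not defined |

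**2. The plan's person-years.** Section 8.6.7 expects 3520–3960 person-years from 1100 patients. 3520/1100 = 3.2 and 3960/1100 = 3.6 years per patient, or 64% and 72% of the maximum 1100 × 5 = 5500. The withdrawal rates behind these figures are not given, so they can be back-calculated but not derived.

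**3. Dilution if the windows differ.** With a constant SAE hazard, events collected only to last dose + 30 days, and all study time in the denominator, the estimated rate is the true rate times

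f = (time on Plegridy + 30 days after stopping) / (time on study).

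Take exponential study withdrawal at hazard w and exponential stopping of Plegridy at hazard d, no restarts, and mean time over 5 years M(h) = (1 − e^(−5h))/h. Setting M(w) = 3.2 gives w = 0.194; M(w) = 3.6 gives w = 0.139. Then, approximately,

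f = M(w + d) × (1 + d × 30/365.25) / M(w).

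Example: 15% stopping per year gives d = −ln(0.85) = 0.1625. With w = 0.194, M(0.3566) = 2.333, so f = 2.333 × 1.0133 / 3.2 = 0.739.

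| Assumed stopping per year | f (mean follow-up 3.2 / 3.6 years) | Understatement of the rate |
|---|---|---|
| 5% | 0.904 / 0.899 | about 10% |
| 10% | 0.817 / 0.808 | 18–19% |
| 15% | 0.739 / 0.726 | 26–27% |
| 25% | 0.604 / 0.587 | 40–41% |
| 35% | 0.495 / 0.475 | 51–53% |

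If 5% and 35% are read as hazards (d = 0.05 and 0.35), the understatement is 9–10% and 45–47%.

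**4. What this does to the estimate.** Assume a true rate of 2 per 100 person-years and 3520 person-years on study, with exact Poisson intervals:

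| f | Events collected | Rate over 3520 person-years (95% CI) | Rate over matched person-years (95% CI) |
|---|---|---|---|
| 1.0 | 70 | 1.99 (1.55–2.51) | the same |
| 0.8 | 56 | 1.59 (1.20–2.07) | over 2816: 1.99 (1.50–2.58) |
| 0.6 | 42 | 1.19 (0.86–1.61) | over 2112: 1.99 (1.43–2.69) |

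Matching the windows removes the dilution whichever window is chosen. The price of the shorter one is a wider interval.

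**5. The incidence proportion.** If each event is in a different patient, 70, 56 and 42 events are 70/1100 = 6.4%, 56/1100 = 5.1% and 42/1100 = 3.8%. The denominator stays at 1100, so a person-time rule cannot repair this. Under the 30-day reading the proportion is not incidence over up to five years of follow-up.

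**The case against.** **The denominator.** A reader might infer that the primary rate divides by full study follow-up and so is biased downward. The protocol does not say this. The wording in 8.6.4.2 is event-specific and could mean the time over which the event was ascertained. Section 8.2.4.5 makes analysis of post-discontinuation data exploratory, which leaves a treatment-window denominator open. The person-years in 8.6.7 are a planning figure. Exact at-risk time is ordinary SAP content. This stands, so the bias is conditional.

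**Capture.** The 30-day sentence does not contain the word only, and the longer rule has strong support. It is hard to argue that late deaths are lost, given 10.2.4.1. Section 10.1.2 also asks for all malignancies to be reported as SAEs, though the 30-day sentence in 10.2.2 names malignancies too. What stands is that non-capture is possible, not established.

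**Relapse endpoints.** It is tempting to extend the point and move ARR and cNEDA to an on-treatment window. The 30-day limit on effectiveness data rests on 8.2.4.4, while the twin paragraph in 8.2.4.9 points only to laboratory assessments. Table 4 also collects other MS therapies after Plegridy through Year 5. An on-treatment window would change what those endpoints estimate, in a study that plans follow-up regardless of discontinuation, and censoring at stopping could be informative. The documents do not support that step.

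**What the objection does not remove.** An SAP can define person-time. It cannot settle which SAEs sites were told to report, and it cannot restore events missing from the incidence proportion.

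**Conclusion.** The point holds as a contradiction in the capture rule for the primary safety endpoint, with a rate denominator that is tied to neither window. That part is certain from the text.

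The size is conditional. A downward bias in the SAE rate of roughly 10% to 50% requires that sites stop collecting at 30 days, that later person-time is counted, that the SAE hazard is constant, that there are no restarts, and that 5% to 35% of patients stop Plegridy per year. The last range is assumed. If SAEs are collected to study end, or person-time stops at last dose + 30 days, this bias in the rate does not arise. If sites differ, its size is unknown. The incidence proportion is affected wherever the shorter window is applied.

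**What to change.** 1. Reconcile 8.2.4.4, 8.2.4.9, 10.2.2, 10.2.4 and 16.1/Table 4 to one SAE capture window for patients who stop Plegridy but stay in the study. Make 8.2.4.4 and 8.2.4.9 point to the same section, and notify sites.
2. State in 8.6.4.2 that numerator and person-time cover that same window: full study follow-up only where SAEs were collected to study end, otherwise time to last dose + 30 days, including restart episodes.
3. State which window the incidence proportion covers.
4. Leave ARR and cNEDA as they are.

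**Cost.** Protocol wording and a site clarification; Plegridy start and stop dates are already collected (8.3.3). Enrollment ended in January 2017, so if the longer window is chosen, sites that applied the shorter one would have to look back through records of patients who stopped. If the shorter window is used, there are fewer person-years and a somewhat wider interval: in the example above, 1.50–2.58 at f = 0.8 against 1.55–2.51 with full capture.

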8.3.6. Effectiveness

The following clinical tests/assessments will be collected to evaluate the effectiveness of Plegridy, if performed under routine clinical practice:

- MS relapse information (e.g., date of onset, date of visit, neurologic examination, duration, new and/or recurrent neurologic symptoms, hospitalization, treatments including steroids), if applicable. For the purposes of this study, relapse is defined as new or recurrent neurologic symptoms not associated with fever, lasting at least 24 hours. New or recurrent neurologic symptoms that evolve gradually over months are to be considered disease progression, not an acute relapse. New or recurrent neurological symptoms that occur fewer than 30 days following the onset of a relapse as defined above are to be considered part of the same relapse.
- EDSS information (including Functional System Scores and Ambulation scores), based on neurological examination, when collected as part of routine clinical practice (i.e. not specifically performed for the study).
- Neurologic assessment, if EDSS is not used in routine clinical practice.
- [REDACTED]
- [REDACTED]
- Details of MS-related hospitalizations (e.g., dates of admission and discharge, reason for admission)
- MRI results (e.g., lesion counts, new lesions/ no new lesions), if available
- Ambulation status during follow-up

Refer to Section 16.1 for the timing of assessments.

CONFIDENTIAL

The information contained herein may not be used, disclosed, or published without the written consent of Biogen MA Inc.

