10.2.3. All Events

All events must be assessed to determine the following:

- If the event meets the criteria for an SAE as defined in Section [10.1.2](#).
- The relationship of the event to study treatment as defined in Section [10.3.1](#).

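### The protocol does not settle whether an uncomplicated relapse leading to hospital admission is a reportable SAE, so the co-primary SAE incidence can vary with physician interpretation

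*Protocol*

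**What the plan says.** Protocol 8.1.1 makes the "incidence proportion and incidence rate of SAEs" a co-primary endpoint. The other co-primary is cNEDA, of which freedom from relapse is one component. Section 8.6.4.2 builds the SAE analysis from reported events: incidence is the share of patients with an event, and the incidence rate is the number of patients with an event adjusted for follow-up.

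Four sections decide what reaches that analysis:

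- **10.1.2** lists the seriousness criteria, among them an event that "requires inpatient hospitalization or prolongation of existing hospitalization". Relapse is not excepted.
- **10.2.3** requires each event to be assessed on this question: "If the event meets the criteria for an SAE as defined in Section" 10.1.2.
- **10.2.4** states: "Any SAE that occurs between the time the patient signs the ICF and study completion or premature study withdrawal must be reported to IQVIA". Again there is no exception for relapse.
- **10.2.2** opens with the same general duty and then says: "MS relapses will not be automatically reported as an SAE unless the relapse was fatal" or, as the second limb, "in the opinion of the Prescribing Physician, the relapse was complicated by other SAEs".

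Section 8.3.6 separately collects, as effectiveness data, relapse information that includes hospitalization, and details of MS-related admissions with dates and reason.

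**The concern.** A relapse that leads to inpatient admission meets the definition in 10.1.2. It cannot be set aside as disease rather than adverse event, because 10.1.1 counts the worsening of a pre-existing condition as an AE. Section 10.2.2 then withdraws *automatic* reporting without saying what replaces it. It does not name admission for the relapse itself as a trigger, and it does not say whether that admission is one of the other SAEs in its second limb.

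At stake is the meaning of a co-primary figure. If some physicians file such relapses and others do not, the result is neither SAEs as 10.1.2 defines them nor SAEs other than relapse. A reader of the SAE tables could not tell how many serious admissions lie outside the count.

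**Working it through.** **Step 1: the passages side by side.** Take a patient admitted for a relapse who recovers with no other serious event.

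| Section | What it implies for this patient |
|---|---|
| 10.1.2 | SAE, because of the inpatient admission |
| 10.2.3 | Must be assessed against 10.1.2, hence an SAE |
| 10.2.4 | Must be reported within 24 hours |
| 10.2.2 | Not automatically reported: not fatal, not complicated by another SAE |

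Three sections lead to a report and the fourth releases the site from an automatic one. A physician who files and a physician who does not can both point to the text.

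**Step 2: the plan's own figures.** The protocol states no expected SAE incidence and no rate of hospitalised relapse. Its rare-event rationale in 8.6.7 does not depend on the relapse rule. For example, an event of 0.10% incidence among 1100 patients gives 1 − 0.999^1100 = 0.667, which matches the stated 67%.

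**Step 3: an illustration per patient, as 8.6.4.2 counts.** Inputs:

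- N = 1100 (8.6.7).
- Share of patients with a relapse in year 1, r: 15% to 31.6%. The upper value is 100% − 68.4%, from the one-year cNEDA assumption in 8.6.7. It is an upper bound because it also contains progression. The 15% is assumed.
- Share of those patients who are hospitalised, h: 5% to 30%, assumed.
- SAE incidence without relapses, b: 10%, assumed, with 5% and 15% as alternatives.

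Formulas: added patients = N × r × h. Inclusive incidence = 1 − (1 − b)(1 − rh), taking the two kinds of event as independent. Half-width = 1.96 × √(b(1 − b)/N).

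- Low end: 1100 × 0.15 × 0.05 = 8.25 patients; 1 − 0.90 × 0.9925 = 10.7%; shift 0.7 points.
- High end: 1100 × 0.316 × 0.30 = 104.3 patients; 1 − 0.90 × 0.9052 = 18.5%; shift 8.5 points.
- Half-width at b = 10%: 1.96 × √(0.09/1100) = 1.8 points.

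| Assumed b | Shift, low to high (points) | Half-width (points) |
|---|---|---|
| 5% | 0.7 to 9.0 | 1.3 |
| 10% | 0.7 to 8.5 | 1.8 |
| 15% | 0.6 to 8.1 | 2.1 |

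These shifts compare counting every hospitalised relapse with counting none. Mixed reporting would fall somewhere between, so they bound its effect under these inputs and do not estimate it. Section 8.6.4.1 analyses Plegridy-naïve and previously exposed patients separately, so the half-width in each group would be wider than shown.

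**The case against.** The strongest reply is that 10.2.2 is a deliberate carve-out. Relapse is an effectiveness outcome, keeping it out of SAE reporting is common practice, and a specific rule ordinarily governs over a general one. On that reading relapses stay outside with two exceptions, and physician opinion enters only the second. This is the most natural reading, and it narrows the point: a reader might infer that SAE incidence is left wholly to each physician's choice, which the text does not support. What remains is that the carve-out is absent from 10.1.2, 10.2.3 and 10.2.4, and that the word *automatically* leaves the uncomplicated admission open.

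Second, the events are not lost. Section 8.3.6 collects them, 8.6.5.4 plans summaries of relapse-related hospitalizations, and coding by MedDRA preferred term would let relapses filed as SAEs be identified. This is right, and it is why the remedy needs no new data. But 8.6.4.2 does not bring these admissions into the SAE analysis. The patient questionnaire behind the 8.6.5.4 summaries, as reproduced in 16.4, asks about admission to nursing homes, hospices or MS centres, so it is not a full substitute for the 8.3.6 record.

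Third, a counting rule belongs in the SAP, which is not at hand. Its absence from the protocol is therefore not held against the plan. The SAP cannot, however, remove a conflict over what sites are told to file.

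Fourth, enrollment ended in January 2017 and this version is dated April 2019, so new wording cannot harmonise forms already filed. That is correct. A uniform rule at analysis still can.

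**Conclusion.** The point holds as a contradiction in the reporting text that leaves a co-primary endpoint without one fixed meaning. Its size is unknown. On assumed relapse, admission and background SAE rates it runs from below the 95% CI half-width (0.7 against 1.8 points) to nearly five times it (8.5 against 1.8).

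Three stronger readings go beyond the documents:

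- A reader might infer that hospitalised relapse is a common event here. No rate is given, and the 31.6% complement of the cNEDA assumption mixes relapse with progression and says nothing about admission.
- A reader might infer that sites did report differently. The text permits this; nothing shows that it happened.
- A reader might multiply an assumed event rate by the 3520–3960 person-years in 8.6.7. That would count events where 8.6.4.2 counts patients. It would also use follow-up after stopping Plegridy, although 10.2.2 and 10.2.4 describe SAE reporting for those patients within 30 days of the last dose.

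Which reporting convention is preferable is not judged here.

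**What to change.** 1. Reconcile 10.1.2, 10.2.3 and 10.2.4 with 10.2.2 so that all four state the same exception and say explicitly how an uncomplicated hospitalised relapse is handled.
2. At analysis, apply one relapse rule to all patients, whether or not a site filed an SAE form.
3. Present the co-primary SAE incidence proportion and rate in two forms: excluding uncomplicated relapse events, and including relapse-related hospitalizations taken from the 8.3.6 data. Count per patient, as 8.6.4.2 defines, and restrict the added admissions to the same observation window in which SAEs are collected.

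The cost is a wording change and one extra row per SAE table, with no new data collection. The inclusive figure will look less favourable.
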